Cognitive Training for Diabetes Self-Management

NCT04831775

March 30, 2022

Study Protocol and Statistical Analysis Plan

Research Design. A pilot RCT will be conducted with 66 adults with T2DM to evaluate the efficacy of the MAPSS-DM intervention to improve the primary outcome of overall cognitive function (e.g. verbal memory performance, use of cognitive strategies) and DM-SM. Drs. [name] and [name] completed a feasibility study of the intervention using a one group pre-test post-test design.¹⁴ This proposed project expands that work by adding a 2-group RCT design with longer follow-up.

Mechanisms to Improve Rigor. The proposed study will reduce bias by 1:1 randomization of participants to the treatment or control group, blinding the data collector to group assignment, training the data collector to follow standardized protocols in collecting data, and randomly monitoring data collection to maintain reliability. Inclusion and exclusion criteria were designed to control for confounding variables. To ensure treatment fidelity, interventionists will be trained using the intervention manual and complete checklists after each class. Strategies for monitoring receipt of treatment (e.g. time spent online, weekly goals) will be used.

Intervention Description. The intervention is composed of 4 small-group webinar classes and home-based individual online cognitive skills practice. The four small-group 2-hr web-based classes are held over 8 weeks. Classes 1 & 2 will focus on common cognitive problems in T2DM and strategies to improve cognitive skills. Classes 3 & 4 focus on lifestyle changes to support cognitive functioning and DM-SM skills. Each online class will follow the same format: (1) introduction/revisiting content from the previous class and answering questions; (2) review of progress on the computer exercises; (3) practicing cognitive strategies in class; and (4) content on weekly topic. The facilitator will review participants' progress on the computer exercises, explore cognitive strategies and difficulties with performance, and prescribe exercises for the following weeks. Each participant will receive a workbook that reemphasizes class content. Intervention fidelity will be increased through use of the intervention manual (tested in PS#2) to ensure all content is covered. The interventionist will be trained by the PI, and will complete a self-assessment checklist after each class to verify content covered.

Computer Training Component. The computer-training component, developed by Posit Science, uses a model for cognitive training that adapts to the user through an integrated hierarchical structure.⁴⁸ The BrainHQ website houses the interactive program that runs on standard web browsers. Participants will only need a computer, smart phone, or tablet with Internet access to securely log onto the website. Each participant will be registered by the research staff using anonymous ID numbers that will allow unlimited access during the study. At the week 1 class, the interventionist will show participants how to log on and access the exercises via a screenshare option provided by the webinar program. The website stores each session a participant completes, and participants will be able to start subsequent sessions wherever they stopped the last time logged on. BrainHQ meets the Institute of Medicine's five requirements for a brain-training program: (1) transferability to other tested tasks; (2) transferability to real-world tasks; (3) evaluation with active control group with access to same product; (4) retention of trained skills; and (5) replication of findings.⁵¹ The intervention group will be asked to practice 20 minutes, 7 days a week.

Comparison Group. Those randomized to the comparison group will receive a referral to the BrainHQ website. A specific amount of practice will not be prescribed, but participants' times and dates of practice will be downloaded from the website. Participants will receive a weekly phone call to maintain connection to the study, but no other intervention. Data collection will be on the same schedule as the intervention group.

Sample and Setting. People with T2DM will be recruited from Texas Diabetes & Endocrinology (TDE) that oversees the health care of over 3500 patients with T2DM per year (see letter of support). About 75% of TDE's patients are female, 36% Hispanic, and 3% African American. [name] has worked with TDE in prior studies. Information about the study will be provided to patients by the TDE health care team and notices will be posted in the clinic. Recruitment materials will instruct participants to call or email the PI for information.

Power analysis. Using data from our preliminary study, a power analysis was run to estimate sample size for the outcomes of decreased A1C, improved cognitive function (i.e. working memory, executive function) using G*Power. For a fully powered randomized trial, assuming a small-to-moderate effect size of $d = .3$, each group would need 64 subjects for the power to be 0.8 at a 0.05 significance level. However, the proposed study is the first comparison test of the MAPSS-DM. A goal of this pilot study is to determine feasibility and to estimate effect sizes. Hertzog has shown that 10–20 subjects per group are often adequate for evaluating feasibility in a pilot study, and 30 subjects are needed when estimating effect sizes.⁴⁹ Allowing for a 10% attrition rate (based on PS#2), 66 persons with T2DM (33 intervention and 33 control) will be recruited.

Recruitment & Enrollment. Inclusion criteria: age 45-70 years old, T2DM diagnosis for 2 years, access to phone and Internet, Score of ≥ 10 on the Perceived Deficits Questionnaire (PDQ), and an A1C of $> 7\%$.⁵⁰ Exclusion criteria: a diagnosis of dementia/head injury, score of > 5 on the Mini-Cog, inability to speak English, and a T1DM diagnosis. For those who indicate interest in participating in the study, a screening assessment will be done either in person or by phone. A script of questions to verify that potential participants meet the inclusion/exclusion criteria will be followed. Participants will be asked the PDQ items that assess self-perceived cognitive difficulties, with questions such as "How often do you lose your train of thought when speaking?" using a 5-point scale ranging from 1 = never to 5 = almost always.⁵⁰ Potential participants must score at least 10 on the PDQ indicating some problems in at least 5 areas to participate. The Mini-Cog will screen potential participants for dementia.⁵¹ A total score of ≤ 5 indicates lower likelihood of dementia. For those who meet the inclusion criteria and agree to participate, a meeting will be scheduled at a time and private location convenient to the participant. Eligible participants will meet with a GRA or PI, who will review the study's purpose and procedures, answer participants' questions, obtain signed consent forms, and collect baseline data.

Randomization. Seven cohorts of 10 subjects will be recruited during the study, and subjects in the cohort will be randomly assigned 1:1 to the intervention or control group using a computer-generated list of random numbers (following baseline testing). The intervention group will be further divided into class sizes of 10-5 participants. In prior cognitive rehabilitation studies, small intervention class sizes (n=10-12) enhanced self-efficacy through vicarious experience and modeling.⁵² In diabetes education, online groups of 10-15 participants have been shown to be effective.⁵²⁻⁵⁴

Data Collection. Questionnaire data will be collected from all participants on an iPad and entered into REDCap at baseline (week 0), at completion of the intervention (week 10), and at 3 months post-intervention (week 22). A GRA who is blind to group assignment will administer the instruments and neuropsych tests in a private location to ensure completion, confidentiality, and privacy. Clinical variables will be gathered by medical record review: current medications, past A1C levels, and co-morbidities. The total data collection time will be about 60 min. Participants will receive a small incentive (\$25) for completing the first two data collections and (\$50) for the final assessment (\$100 total). Data will be downloaded for analysis into IBM SPSS Statistics version 23.⁵⁵ All intervention participants will be invited to join a focus group after their final data collection to evaluate their perceptions of the acceptability of the MAPSS-DM intervention.

Table 1. Physiological Measures (pre- and post-intervention at week 2 and week 22)		
A1C	Medical record	The national standard measure of glycemic control over a 3-month period.
BMI	Weight, height	kg/m ²
Self-Report Measures (pre- and post-intervention) Time to Administer ~30 minutes for this battery		
Demographics	Background information	Age, gender, years with DM, ethnicity/race, socioeconomic status, history of DM education, years of education
DM-SM	Summary of Diabetes Self-Care Activities ⁵⁶	18 items; Participants answer "how many days in the last week..." they performed DM self-management such as diet and physical activity. Inter-item correlations range from $r = 0.20$ to 0.76 for four SDCA subscales; 4-month test-retest reliability range from $r = -0.05$ to 0.78 .
Self-efficacy	Diabetes Empowerment Scale – Short Form ⁵⁷	8 items; Brief assessment of diabetes related psychosocial self-efficacy. Responses are made on a 5-point scale (1 = strongly disagree to 4 = strongly agree) to items such as "I believe that I am able to turn my diabetes goals into a workable plan." Cronbach's alphas range from 0.81 to 0.96.
Depression	CES-D ⁵⁸	20 items; measures depressive symptoms. 4-point item response scale from rarely/none of the time to most/all of the time in 8 health dimensions: role limitations due to physical problems, social functioning, physical functioning, bodily pain, general mental health, role limitations due to emotional problems, vitality, and general health perceptions. Internal consistency ranged from 0.85 to 0.91 and test-retest reliability ranged from 0.45 to 0.70.
Perceived Cognitive Function	PROMIS v2.0 – Cognitive Function ⁵⁹	32 items; assess patient-perceived cognitive deficits including the areas of mental acuity, concentration, verbal and nonverbal memory, and verbal fluency. Reliability has been measured at 0.94 and test-retest correlation at 0.83. (Becker 2014)
Objective Cognitive Function Measures (pre- and post-intervention) ~ 35 minutes to administer		
Episodic memory	Picture Sequence Memory (NIH-Toolbox) ⁶⁰	Assessment of episodic memory. It involves recalling increasingly lengthy series of illustrated objects and activities presented in a particular order on the computer screen. Participants are asked to recall the sequence of pictures demonstrated over two learning trials. Participants are given credit for each adjacent pair of pictures (i.e., if pictures in locations 7 and 8 and placed in that order and adjacent to each other anywhere – such as slots 1 and 2 – one point is awarded) they correctly place, up to the maximum value for the sequence, which is one less than the sequence length (if there are 18 pictures in the sequence, the maximum score is 17, because that is the number of adjacent pairs of pictures that exist).

Executive Function and Attention	Flanker Inhibitory Control and Attention (NIH-Toolbox) ⁶⁰	Measures both a participant's attention and inhibitory control. The test requires the participant to focus on a given stimulus while inhibiting attention to flanking it. Scoring is based on a combination of accuracy and reaction time.
Working memory	List Sorting Working Memory (NIH-Toolbox) ⁶⁰	Assesses working memory. Requires the participant to sequence different visually- and orally-presented stimuli in two different conditions. In the 1-List condition, participants are required to order a series of objects (either food or animals) in size order from smallest to largest. In the 2-List condition, participants are presented both food and animals and are asked to report the food in size order, followed by the animals in size order.
Processing speed	Pattern Comparison Processing Speed (NIH-Toolbox) ⁶⁰	This measures speed of processing by asking participants to discern whether two side-by-side pictures are the same or not. Participants' raw score is the number of items correct in a 90-second period.
Attention, visual scanning, and motor speed	Symbol Digit Modalities Test ⁶¹	Participants are given a series of symbols and digits and instructed to verbalize the digit associated with each symbol. The number of correct responses in 90 sec constitutes the score, and higher scores reflect better cognitive function.

Glucose Variability. Participants will wear CGMS devices for one week at specific intervals (week 0, week 5, week 11, and week 22). Abbott's FreeStyle Libre CGMS consists of a small, round sensor about the size of two stacked U.S. quarters—worn on the back of the upper arm for up to 14 days, which measures glucose every minute in interstitial fluid through a small (5mm long, 0.4mm wide) filament that is inserted just under the skin and held in place with a small adhesive pad.⁶² A reader is scanned over the sensor to get a glucose result painlessly in less than one second. Each scan displays a real-time glucose result, a historical trend and the direction the glucose is heading. Participants will scan the sensors at least 2 times a day. CGMS data will be downloaded at each data collection visit. The stored amperometric data from the monitor will be transferred and converted to glucose concentrations after data collection is completed using an infrared link to a personal computer and are analyzed using the CGMS solution software which will be maintained by the research staff. The FreeStyle Libre system generates an Ambulatory Glucose Profile (AGP) that provides a visual snapshot of glucose levels, trends and patterns over time. The following five glucose composites will be calculated: (1) the overall mean, (2) the proportion of readings indicating hypoglycemia (% <70mg/dL), (3) the proportion of readings indicating hyperglycemia (% >160mg/dL), (4) the proportion of out of range readings (% either <70mg/dL or >160mg/dL) and (5) the SD of CGM glucose readings.⁶³ Compared with SMBG, 85.5% of FreeStyle Libre readings were clinically accurate and 99.0% were clinically acceptable on a Clarke error grid, using linear mixed modelling.

Statistical significance. The data will be evaluated for violations of statistical tests. If assumptions are violated, alternative tests will be used or the data will be transformed. Individual t-tests will be run on the baseline variables (e.g. A1C, cognitive function tests) to determine if significant differences exist between the intervention and control groups, and we will control for those baseline differences in subsequent analyses. Analysis will follow intent-to-treat principles. Correlations will examine the relationships between the major variables. The significance level will be .05 for each test.

Statistical Analyses. For Aim 1, we will use multilevel longitudinal models to estimate MAPSS-DM treatment effects on A1C, DM-SM and measurements of memory and executive function over time. Multilevel longitudinal models are generalizations of repeated-measures ANOVA that include every participant in the analysis, regardless of missing data, and will account for the clustering of measurements within participants. The model will also contain fixed effects for intervention (MAPSS-DM vs control) interacted with measurement occasion (baseline, 8 weeks, 3 months), as well as for cohort and baseline covariates. We will use the models to test for overall treatment effects ($p < 0.05$), effects at each post-baseline time-point, and within-subject effects. Effect sizes will be expressed as Cohen's d. Additionally, We will use causal-mediation methods and exploit the longitudinal structure of the data collection to estimate the mediational role of cognitive function. We will regress each cognitive function measurement at 8 weeks (post-intervention) on the group assignment (MAPSS-DM or control), the same cognitive measurement at baseline, and demographic controls.^{v&V2014} These regressions estimate the effect of the intervention on cognitive function at week 8. Next, we will regress the 3-month A1C and adherence measures at 3-months on the same variable at baseline, group assignment, cognitive measurements at week 8, and demographic controls. The average mediated effect of the intervention on A1C or adherence will be estimated by the sum of the coefficients on intervention from the first set of regressions multiplied by the coefficients on the corresponding cognitive measurements in the second regression, with Monte-Carlo confidence intervals and statistical tests.⁶⁴ For Aim 2, CGMS data will be downloaded at each data collection visit. Within subject change in the mean values of CGMS summary variables between pre-, during and post-intervention will be determined. The percentage of time spent in low

(<70mg/dL), normal (71mg/dL – 120mg/dL) and high (>160mg/dL) will be calculated. We will use analogous regression models to those in Aim 1 to estimate the effect of the intervention on glucose variability at post-baseline time-points, and mediational role of the of glucose variability in the intervention's effect on cognitive functions.

Potential sources of biological variation. To address the issue of potential differences in cognitive function, A1C, glucose variability, and DM-SM adherence between men and women, we will re-fit appropriate regression models from the analyses and include interaction terms between intervention group and sex.

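### The cognitive half of the primary outcome has no defined score or visit, its two examples have no matching instrument, and every outcome is tested at .05 with no order among the tests

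*Combined protocol and SAP*

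**What the plan says.** Research Design states that the trial will evaluate efficacy on "the primary outcome of overall cognitive function (e.g. verbal memory performance, use of cognitive strategies) and DM-SM". It gives no instrument, score or time point for either part.

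Table 1 lists what is collected:

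- **Objective cognition:** Picture Sequence Memory, Flanker, List Sorting, Pattern Comparison and Symbol Digit Modalities.
- **Perceived cognition:** the PROMIS questionnaire, which includes verbal memory as the patient perceives it.
- **DM-SM:** an 18-item self-care scale with four subscales mentioned.
- **A1C:** from the medical record.

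The Power analysis section names a different set: "outcomes of decreased A1C, improved cognitive function (i.e. working memory, executive function) using G*Power". Statistical Analyses, for Aim 1, names a third: "treatment effects on A1C, DM-SM and measurements of memory and executive function over time". That section tests an overall treatment effect at p < 0.05, effects at each post-baseline visit, and within-subject effects. Statistical significance sets the error rule: "The significance level will be .05 for each test". No testing order or multiplicity adjustment appears.

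**The concern.** A primary outcome settles in advance which single result decides the efficacy question. Here the cognitive part is a construct with no calculation attached, and the two examples meant to illustrate it point to things the battery does not capture. The three sections that should agree on the outcomes do not, and each outcome carries its own .05. Someone who sees the results could in good faith present Flanker, List Sorting, Picture Sequence, DM-SM or A1C as the finding that matters.

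Two things are at stake. One is the false-positive rate of any efficacy statement. The other is the effect size carried into the next trial: an estimate picked because it was the largest of several will tend to be too large, and estimating effect sizes is one of this pilot's stated goals.

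**Working it through.** **1. Outcome lists side by side**

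| Outcome | Research Design (primary) | Power analysis | Aim 1 model | Instrument in Table 1 |
|---|---|---|---|---|
| Overall cognition | yes | no | no | no composite defined |
| Verbal memory performance | as example | no | not named | none objective; PROMIS covers it as perceived |
| Use of cognitive strategies | as example | no | no | none |
| Working memory | no | yes | under memory | List Sorting |
| Executive function | no | yes | yes | Flanker |
| DM-SM | yes | no | yes | self-care scale, score not chosen |
| A1C | no | yes | yes | medical record |

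The one objective episodic memory test uses pictures.

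**2. The plan's own figure.** The Power analysis section says that at d = 0.3 "each group would need 64 subjects for the power to be 0.8 at a 0.05 significance level". For a two-sided, two-group t-test, d = 0.3 needs 176 per group; 64 corresponds to d = 0.5 (63.8, rounded up). That is a separate matter. It does not set the 66 recruited, which rests on 30 per group for effect-size estimation plus 10% attrition (30 × 1.1 = 33 per arm). The outcome mismatch in that paragraph therefore does not change N.

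**3. How many tests.** The documents give no count, so it is an assumption. Reading the Aim 1 sentence by Table 1's labels gives about five: A1C, DM-SM, Picture Sequence, List Sorting and Flanker. All five objective tests plus DM-SM give six; adding A1C gives seven.

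**4. Chance of at least one false positive at one visit.** If independent, this is 1 − 0.95^k. For correlated tests, k equally correlated two-sided z-tests were simulated (400,000 draws); the correlations are assumed.

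| k | independent | r = 0.3 | r = 0.5 | r = 0.7 |
|---|---|---|---|---|
| 5 | 22.6% | 20.9% | 18.3% | 14.8% |
| 6 | 26.5% | 24.1% | 20.8% | 16.4% |
| 7 | 30.2% | 27.1% | 23.0% | 17.8% |

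Testing both post-baseline visits doubles k. For 10 to 14 tests the rate is 40%–51% if independent and 21%–44% at r = 0.7 to 0.3. Even restricting the claim to two named primaries, each at .05, gives 1 − 0.95² = 9.75% if independent.

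**5. What a composite would do.** Inputs: 30 completers per arm, two-sided .05, unadjusted t-test, and the plan's d = 0.3. One test has power 21%. For the mean of five standardised tests with pairwise correlation r, of which m shift by 0.3 SD, d = (0.3m/5) / √((1 + 4r)/5).

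- All five shift: r = 0.2 gives 0.3/0.600 = 0.50, power 48%; r = 0.5 gives 0.3/0.775 = 0.39, power 31%.
- Two shift: r = 0.2 gives 0.12/0.600 = 0.20, power 12%; r = 0.5 gives 0.12/0.775 = 0.155, power 9%.

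Adjusting for baseline raises power. With an assumed baseline correlation ρ, d becomes 0.3/√(1 − ρ²). For a single test, ρ = 0.5 gives 0.346 and 26%; ρ = 0.7 gives 0.420 and 36%.

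**The case against.** The best defence is that this is a pilot. The Power analysis section gives feasibility and effect-size estimation as a goal, and Aim 1 already expresses effects as Cohen's d. In a purely estimating study, unadjusted .05 tests do little harm. This softens the point but does not remove it, because Research Design states an efficacy purpose and Aim 1 tests treatment effects at p < 0.05.

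A second defence is that the examples are introduced only as examples, so a missing instrument for them does not leave cognition unmeasured. That is correct. A reader might infer that the primary outcome is not measured at all, or that the trial cannot report it. The documents do not support that: cognition has five objective tests and PROMIS and can be reported domain by domain, while DM-SM has its own scale and is in the Aim 1 model. What cannot be reported as planned is a single overall cognitive result.

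A reader might also take six or seven tests, and hence 26%–30%, as a property of the plan. It is one count among several. The literal Aim 1 reading gives about five, and counting PROMIS, self-care subscales or both visits gives more.

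Finally, a composite is not plainly better than a single test. It gains power if the effect is spread across all five tests, and loses it if only the two domains named in the Power analysis section move.

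**Conclusion.** The point holds in limited form. The cognitive primary lacks a score and a visit, its two examples lack matching instruments, the DM-SM score is not chosen, and three sections list three different outcome sets. DM-SM is primary and modelled but absent from the power paragraph; A1C is in the power paragraph and modelled but not named primary. Combined with .05 for each test and no order, this leaves the deciding result open until the data are seen.

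The false-positive rate for a claim based on any one outcome is roughly three to six times the nominal 5% at one visit: 23%–30% under independence and about 15%–27% with correlations of 0.3–0.7. Both the five-to-seven count and the correlations are assumptions. The matter should be corrected, but it does not invalidate a pilot of this size, and it has no bearing on the 66 recruited.

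**What to change.** Before any unblinded analysis:

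1. Name one cognitive primary from the data already collected: either a single listed test, or the mean of the five objective tests standardised to baseline mean and SD.
2. Name one post-intervention visit, after reconciling week 10 in Data Collection with 8 weeks in Statistical Analyses.
3. Keep DM-SM as the other primary with one stated score, and control error across the two by a fixed order, Holm, or split alpha (0.05/2 = 0.025 each).
4. Delete the verbal memory and strategy-use examples from the primary outcome, and make Research Design, Power analysis and Statistical Analyses list the same outcomes.
5. Report all other outcomes, A1C included, as Cohen's d with 95% confidence intervals and no significance claims.

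This costs plan wording and, if the composite is chosen, one derived variable; no new data are needed. The downside is that fewer results can support an efficacy claim. A composite also loses power if only one or two domains change: about 9%–12% in the two-of-five case worked above. The choice between a single test and a composite should follow from where the team expects the effect.

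### The assessment calendar names no A1C for the end-of-intervention effect that the Aim 1 model tests, and the cognitive primary outcome has no designated measure

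*Combined protocol and SAP*

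**What the plan says.** **Timing.** Data Collection schedules assessments "at baseline (week 0), at completion of the intervention (week 10), and at 3 months post-intervention (week 22". The header over A1C and BMI reads "Table 1. Physiological Measures (pre- and post-intervention at week 2 and week 22". A1C comes from the medical record; Data Collection mentions chart review of past values but gives no rule for which draw belongs to which visit.

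Statistical Analyses lists A1C, DM-SM and measures of memory and executive function as Aim 1 outcomes. The group effect is interacted with "measurement occasion (baseline, 8 weeks, 3 months", and the tests include "effects at each post-baseline time-point, and within-subject effects". For mediation the plan states: "We will regress each cognitive function measurement at 8 weeks (post-intervention) on the group assignment". It then says it will "regress the 3-month A1C and adherence measures at 3-months on the same variable at baseline". On programme length, Intervention Description says: "The four small-group 2-hr web-based classes are held over 8 weeks".

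**Primary outcome.** Research Design names overall cognitive function and DM-SM. It describes the cognitive part only by two examples, verbal memory and strategy use. Power analysis refers to working memory and executive function. Table 1 lists four NIH Toolbox tests, the Symbol Digit Modalities Test and the self-report PROMIS scale. None is marked primary and no composite is defined. Statistical significance sets .05 for every test.

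**The concern.** An effect can be estimated at an occasion only if values are assigned to it. The Aim 1 model asks for an A1C contrast at the end of the intervention, but the only A1C weeks named are 2 and 22. An analyst would have to choose chart values for that occasion after the fact. Because Table 1 describes A1C as reflecting about three months of glycaemia, the draw date decides how much of the programme a value covers.

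For the cognitive primary, up to six measures could be put forward, each tested at .05, so a favourable one could be presented as the primary result. The stakes are lower in a pilot that aims at feasibility and effect sizes. Even so, Research Design sets out to evaluate efficacy, the models test at p < 0.05, and an effect size carried into a later trial needs a defined outcome and time point.

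**Working it through.** The plan states no figure on this point. The checks are a side-by-side reading, week arithmetic and an error-rate calculation.

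**1. Calendars compared**

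| Source | Before | End of programme | Follow-up |
|---|---|---|---|
| Data Collection | week 0 | week 10 | week 22 |
| Table 1, A1C and BMI | "pre" value, or week 2 | none named | week 22 |
| Aim 1 models | baseline | 8 weeks | 3 months |
| Glucose Variability (sensor) | week 0 (and week 5 during) | week 11 | week 22 |

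The visit schedule agrees with itself: 10 + 12 = 22. From an 8-week anchor, three months later is week 20 or 21 (8 + 12 or 8 + 13), and 22 − 8 = 14 weeks. So the models' 3 months fits week 22 only if their 8 weeks means the week-10 visit. No visit falls at week 2 or week 8.

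**2. Readings of the Table 1 header**

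- Before = week 2 and after = week 22: no end-of-programme A1C.
- A pre-programme value plus weeks 2 and 22: again none.
- Week 2 counted from the end of the 8 weeks of classes: 8 + 2 = 10, which would supply the value. This mixes two clocks in one header, and no text supports it.

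A misprint is also possible, but the intended week is not stated.

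**3. What is unaffected.** The outcome regression in the mediation analysis uses A1C at baseline and 3 months only. The week-22 A1C effect needs no middle value. In the mediation analysis, only the week label of the cognitive mediator needs correcting.

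**4. Cognitive measures.** Memory and executive function, as named for Aim 1, map to three Table 1 tests: Picture Sequence Memory, List Sorting and Flanker. All cognitive measures together number six (five objective tests plus PROMIS). With one test per measure at .05, the chance of at least one false positive if independent is 1 − 0.95^k:

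- k = 3: 1 − 0.95³ = 0.143
- k = 6: 1 − 0.95⁶ = 0.265

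Simulated with an assumed common correlation of 0.5, these become 0.125 and about 0.21.

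**5. Sensitivity if week 2 were used as the A1C baseline.** Assumptions: a 13-week A1C window and an effect that persists to week 22. The share of the week-22 effect lost is the part of the week-2 value that already reflects the programme.

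| Programme start | Immediate effect, equal weights | Immediate effect, linear recency weights | Effect building over 8 weeks (equal; recency) |
|---|---|---|---|
| week 0 | 2/13 = 0.154 | 1 − (11/13)² = 0.284 | 0.019; 0.036 |
| week 1 | 1/13 = 0.077 | 1 − (12/13)² = 0.148 | 0.005; 0.009 |
| week 2 | 0 | 0 | 0; 0 |

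The start week on the visit clock is not given. Computer Training Component says "At the week 1 class, the interventionist will show participants how to log on and access the exercises", without saying which clock it uses.

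**6. A1C values a draw-date rule might retain.** After 10% attrition, 33 × 0.9 = 29.7 per group. Assume regular draws at a random phase, so that the share captured is window width divided by draw interval. The clinic's interval is not given; 13 and 26 weeks are shown as a range, and the windows are illustrative.

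- Weeks 10 to 16: 6/13 × 29.7 = 13.7, or 6/26 × 29.7 = 6.9 per group.
- Weeks 18 to 26: 8/13 × 29.7 = 18.3, or 8/26 × 29.7 = 9.1 per group.

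**The case against.** The strongest reply is that these are labelling slips in a pilot. Chart A1C needs no study visit, record review is described alongside the 0/10/22 schedule, the multilevel model tolerates missing values, and A1C is not in the stated primary outcome. Much of this is fair. The absence of a week-10 A1C visit is not itself the defect; the absence of a rule assigning chart values to occasions is. The model's tolerance of gaps does not help if an occasion has no assigned values at all.

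On cognition, working memory is a form of memory, so Power analysis and the Aim 1 list are compatible, and PROMIS does cover verbal memory by self-report. Both points stand. They still leave no objective verbal-memory test, no instrument for strategy use and no designated measure.

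A reader might go further and infer three things that the documents do not support:

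- *That a week-2 baseline would erase up to 28% of the A1C effect.* Data Collection puts baseline at week 0, randomisation follows baseline testing, and both the A1C entry criterion and the planned baseline comparison imply a value before randomisation. The loss ranges from 0% to roughly 28% under the weightings tried, none of which is a bound, and is under 4% if the effect builds over 8 weeks.
- *That the A1C mediation analysis fails.* It does not use a middle A1C.
- *That the false-positive risk is 27%.* That requires all six measures to be eligible and independent, which goes beyond the outcomes named for Aim 1.

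**Conclusion.** Both parts hold and should be fixed before analysis. The calendar contradiction is a matter of text and needs no assumption: as written, the end-of-intervention A1C contrast has no named value and no rule for finding one. No reliable figure can be put on the resulting bias, and the week-2 baseline calculation should not be used as one.

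The undesignated cognitive primary raises the chance of at least one false positive from 5% to about 14% over three tests if independent (about 13% at an assumed correlation of 0.5), with 27% (21%) as the upper case over six. These figures count one test per measure. The pilot's aims lower the consequences but do not remove the need for a defined outcome and time point.

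**What to change.** 1. Put Table 1 and the Aim 1 models, including the mediator regressions, on the week 0, 10 and 22 visits. Correct or explain week 2. Keep the Aim 2 sensor models on weeks 0, 5, 11 and 22, as Glucose Variability has them; moving those to the visit calendar would create a new conflict.
2. Use the last A1C before randomisation as baseline. Prespecify a draw-date rule for assigning chart values to week 10 and week 22, set after checking the clinic's draw interval. If too few values would fall near week 10, model A1C at baseline and week 22 only and drop the end-of-intervention A1C contrast.
3. Designate one collected cognitive test or a prespecified composite, one DM-SM score (an instrument is named, but no subscale or total is chosen) and one primary time point. Label the other cognitive measures secondary. Two primaries at .05 each still give 1 − 0.95² = 0.0975 if independent, so either control error across them, for example by Holm, or state that p-values are descriptive in this pilot.

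The cost is mostly wording, plus chart review beyond week 22 if the rule accepts later draws. The real downside is missing A1C values: the illustrative counts above (about 7 to 18 per group) fall well below the 30 that Power analysis cites for estimating effect sizes. This can affect week 22 as well as week 10, so each A1C effect size should be reported with the number of values behind it. The sample size does not change.
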